### 4 Study design

### 4.1 Overall design

This is an open-label, single arm, two-stage study to evaluate the efficacy and safety of bimiralisib in patients with r/m HNSCC containing *NOTCH1* LOF mutations. The study will be conducted in 1 - 4 centers.

Patients will be treated with 140 mg bimiralisib p.o. once daily on two consecutive days followed by 5 days without treatment in consecutive 7-day treatment blocks. Patients will continue this iterative "2d on / 5d off" treatment scheme until unacceptable toxicity, tumor progression, patient's request for withdrawal, investigator judgment or death, whichever comes first. The bimiralisib dose may be decreased to 100 mg p.o. administered on the same dosing schedule in order to manage safety and/or tolerability (see section on dose interruptions and modifications, section 7.2). Changes in dosing schedule are not allowed.

Stage 1 of the study will enroll 10 patients. Response evaluation of Stage 1 patients will be performed in an ongoing manner (ongoing analysis, OA). If two or more patients in stage 1 show a confirmed partial or confirmed complete response, Stage 2 may enroll 19 patients. Conversely, Stage 2 may not start if only one or no patients in Stage 1 have shown a confirmed partial or confirmed complete response.

If patients withdraw consent or drop out for other reasons unrelated to safety or disease progression, they may be replaced. This includes patients who start smoking (as evidenced by cotinine test) within the first 12 weeks on bimiralisib treatment, because smoking is known to severely compromise bimiralisib exposure due to induction of CYP1A2, the main metabolizing enzyme of bimiralisib. These patients may remain on treatment but will be replaced. Patients for whom IHC analyses indicated high protein levels of NICD which are deemed incompatible with NOTCH1 loss-of-function may be replaced. In total, we anticipate up to 20% of patients to drop out, resulting in enrollment of up to 35 patients in total.

The study will end when all patients have been treated for at least 6 months or have discontinued study participation for any reason, whichever comes first.

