## Table 4: Treatment interruptions and dose reductions for adverse events (except hyperglycaemia) considered related to bimiralisib by the treating physician

Reason	Treatment change
Non-haematological AE Grade 4	Stop bimiralisib treatment permanently.
Haematological AE Grade 4	Interrupt bimiralisib treatment. If AE resolves to baseline or CTCAE grade 1 within 7 days, patients may resume treatment at the reduced dose of 100mg. If AE resolves within 8 to 14 days, patient may resume treatment at the reduced dose of 100mg if agreed between investigator and sponsor. If AE does not resolve to baseline or CTCAE grade 1 within 14 days, bimiralisib treatment must be discontinued permanently.
Grade 3 AE	Interrupt bimiralisib treatment. If AE resolves to baseline or CTCAE grade 1 within 7 days, patient may resume treatment at 140mg. If AE resolves to CTCAE grade 1 within 8 to 14 days, patient may resume treatment at the reduced dose of 100mg. If AE does not resolve to baseline or CTCAE grade 1 within 14 days, bimiralisib treatment must be discontinued permanently.
Any non-haematological AE grade 2	Continue bimiralisib treatment. Dose reduction at the discretion of the treating physician

Patients who after dose interruption do not tolerate bimiralisib treatment at 100 mg must be permanently discontinued. If during the first three months on study, a patient cannot restart at the 100 mg dose level within 14 days, this patient is not evaluable for the primary endpoint, and the investigator must discuss the individual benefit-risk evaluation of this patient with the sponsor before restarting dosing. These patients may be replaced.

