# **10.2** Sample size determination

To minimize accrual if bimiralisib is ineffective, a Simon's optimal two-stage design is used. In order to have 80% power to detect a response rate of 30%, (one-sided  $\alpha$ =0.05 and  $\beta$ =0.20) up to 10 patients will be enrolled in the first stage. If 1 or 0 patient respond to the treatment, the trial will be closed due to futility and the treatment is considered ineffective. If two or more patients have an objective response, the study will enroll an additional 19 patients in the second stage. The null hypothesis (H0: ORR  $\leq$  10%) will be rejected if the number of responses is  $\geq$  6 in 29 patients.

If patients withdraw consent or drop out for other reasons unrelated to safety or disease progression, they may be replaced (see section 9.11). We anticipate up to 20% of patients to drop out, resulting in enrollment of up to 35 patients in total.

This sample size is also reasonable to evaluate the pharmacokinetic and other correlative science endpoints; yet, no explicit sample size justification is made for these exploratory endpoints.

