# 10.3.2 Per-protocol set

The per-protocol set (PPS) consists of a subset of the safety set who are compliant with requirements of the clinical study protocol. All protocol deviations or conditions leading to exclusion from the PPS will be detailed in the data handling plan and statistical analysis plan.

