# **10.4.1** Efficacy analyses

All efficacy analyses will be performed on the PPS.

ORR including confirmed complete response (CR), and confirmed partial response (PR) is the primary endpoint.

Frequency and percentage of the ORR with a two-sided 95%-confidence interval will be determined.

Secondary endpoints include additional clinical efficacy assessment by time to response (TTR), duration of response (DOR), time to treatment failure (TTF) and progression-free survival (PFS).

Time to event data will be summarized using the Kaplan-Meier methodology.

Time to response (TTR) is defined as the time from first study drug administration to the first documentation of response (complete or partial).

Duration of response (DOR) is defined as the time from the date of the first confirmed response to the first documentation of disease progression, whichever occurs first

Progression- free survival (PFS) is defined as the time from first study drug administration to disease progression or death due to any cause.

Time to treatment failure (TTF) is defined as the time from first study drug administration to any treatment failure including disease progression or discontinuation of treatment for any reason (e.g., disease progression, AE, patient withdrawal of consent, initiation of new treatment without documented progression, death)

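### Section 7.2 takes early drug-toxicity failures out of the primary ORR denominator and lets them be replaced, against the replacement rule in 4.1, 9.11, 10.2 and SAP 1.2

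*Protocol*

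**What the plan says.** Table 4 in protocol section 7.2 covers adverse events, other than hyperglycaemia, that the treating physician attributes to bimiralisib. For grade 3 and for haematological grade 4 events it ends with this rule: "If AE does not resolve to baseline or CTCAE grade 1 within 14 days, bimiralisib treatment must be discontinued permanently". The paragraph below the table adds that if, during the first three months, "a patient cannot restart at the 100 mg dose level within 14 days, this patient is not evaluable for the primary endpoint". The investigator "must discuss the individual benefit-risk evaluation of this patient with the sponsor before restarting dosing", and then: "These patients may be replaced".

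The general replacement rule reads differently. Section 4.1 has "If patients withdraw consent or drop out for other reasons unrelated to safety or disease progression, they may be replaced", and section 9.11 says the same. Section 10.2 and SAP 1.2 carry the same condition: "drop out for other reasons unrelated to safety or disease progression, they may be replaced". Sections 4.1 and 9.11 then name two special cases, patients who start smoking in the first 12 weeks and patients with high NICD protein. Neither names toxicity.

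On analysis sets, section 10.4.1 says "All efficacy analyses will be performed on the PPS". Section 10.3.2 defers the exclusions: "All protocol deviations or conditions leading to exclusion from the PPS will be detailed in the data handling plan and statistical analysis plan". The SAP text available contains only the hypotheses and the sample size. No ORR in all treated patients is specified.

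**The concern.** A patient who has to stop early because of drug toxicity, without a response, is a treatment failure. Section 7.2 treats that patient as missing and allows another to be enrolled instead.

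The direction of the bias is predictable. Under section 9.3 a confirmed response needs at least two on-treatment assessments, the first two at day 43 and day 85. A patient stopped for toxicity in the first three months will rarely have reached confirmation, so the rule removes mostly non-responders, and for a reason caused by the drug.

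Both decision rules are fixed counts: at least 2 responses in 10 to open stage 2, and at least 6 in 29 to reject H0. Exclusion alone raises the reported percentage. Exclusion with replacement also gives extra chances to reach both counts. Whether to replace is left to discretion, in an open-label study whose responses are reviewed as they accrue.

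There is also a practical conflict. For a patient stopped under Table 4, section 7.2 permits replacement, while section 9.11, the section devoted to replacement, gives no ground for it.

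**Working it through.** **Inputs from the documents.** Null ORR 10%, alternative 30%, one-sided α 0.05, power 80%. Stage 1 has 10 patients and continues with 2 or more responses; stage 2 adds 19; H0 is rejected with 6 or more responses in 29 (sections 10.1 and 10.2, SAP 1.1 and 1.2). Planned maximum enrolment is 35.

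**Input assumed.** The share *f* of treated patients who become non-evaluable under 7.2 without having responded. The documents give no such rate, so 5% to 20% is shown.

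**Step 1: the plan's own design.** With response probability p,

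P(reject | p) = Σ over x = 2…10 of P(X₁ = x) · P(X₂ ≥ 6 − x), where X₁ ~ Bin(10, p) and X₂ ~ Bin(19, p).

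This gives 0.0471 at p = 0.10 and 0.8051 at p = 0.30. A search over designs confirms that this is the Simon optimal design for these inputs. The stated design is correct, provided that p is the response rate of the patients being counted.

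**Step 2: effect of the 7.2 rule.** If a share f of treated patients are non-responders who are removed and replaced, the rate among the patients counted is p_eval = p / (1 − f). For a true all-treated ORR of 10%:

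| f | p_eval = 0.10/(1 − f) | P(at least 2 of 10) | P(reject H0) | P(reject H0), enrolment capped at 35 | Expected replacements, 29f/(1 − f) |
|---|---|---|---|---|---|
| 0 | 0.1000 | 0.264 | 0.047 | 0.047 | 0 |
| 5% | 0.1053 | 0.284 | 0.058 | 0.058 | 1.5 |
| 10% | 0.1111 | 0.307 | 0.071 | 0.071 | 3.2 |
| 15% | 0.1176 | 0.333 | 0.088 | 0.084 | 5.1 |
| 20% | 0.1250 | 0.361 | 0.110 | 0.095 | 7.3 |

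The capped column follows patients one at a time, each being a responder (0.10), a replaced toxicity case (f) or another non-responder (0.90 − f). It stops at 29 evaluable or 35 enrolled and still requires 6 responses. The error passes 0.05 at about f = 1.5%.

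**Step 3: effect on the estimate.** Six responses among 29 evaluable patients is 6/29 = 20.7% (exact 95% CI 8.0% to 39.7%). If six further patients were treated and removed, the all-treated figure is 6/35 = 17.1% (6.6% to 33.6%).

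**Step 4: who is covered.** The sentence in 7.2 names no type of adverse event and does not repeat the hyperglycaemia exception in the title of Table 4. Section 12.6.1.1 lets a patient whose grade 3 or 4 hyperglycaemia improves within 21 days restart at the reduced dose. Read literally, a patient restarted on day 18, as 12.6.1.1 permits, becomes non-evaluable. The reference to restarting dosing also fits poorly with Table 4, which requires permanent discontinuation when the event has not resolved by day 14.

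**The case against.** - **The target could be the ORR in evaluable patients.** Efficacy is analysed on the per-protocol set, and for that quantity the error stays at 0.047. But section 10.1 states the goal as the ORR in patients with NOTCH1-mutated disease, not in those who tolerate the drug, and the general replacement rule makes no provision for replacing safety failures.
- **The replacement rule never says that its grounds are the only ones.** Section 7.2 could then be one more special case. Even so, 9.11 lists the other special cases and omits this one, so the documents still need reconciling.
- **The scope is limited.** The rule applies only in the first three months. For patients who restart and then do not tolerate 100 mg, section 7.2 states no loss of evaluability. The wording about restarting could mean delayed restarts only, though a patient whose event has not resolved literally cannot restart. The hyperglycaemia reading is the weaker one. These points stand and limit the number affected.
- **The figures assume that every excluded patient is a non-responder.** If excluded patients responded at 5%, then p_eval = (0.10 − 0.05f)/(1 − f), and the error for f of 5%, 10%, 15% and 20% is 0.052, 0.058, 0.066 and 0.075. If they responded at 10% there would be no inflation. At f = 20% the expected 7.3 replacements exceed the six extra places (35 − 29), which must also serve other drop-outs, so the capped 0.095 is the better figure there.
- **The change may cost power.** If the 30% target was meant for evaluable patients, counting 10% or 20% toxicity non-responders gives an all-treated ORR of 0.30 × 0.90 = 27% or 0.30 × 0.80 = 24%, with power 0.720 or 0.610 instead of 0.805.

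**Conclusion.** The concern holds. As written, 7.2 removes a group of drug-toxicity failures from the primary denominator, allows them to be replaced, and conflicts with the replacement rule stated in four other places. Nothing else in the plan corrects for this.

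Against an all-treated ORR of 10%, the one-sided error rises from 0.047 to between 0.058 and 0.095 within planned enrolment, if 5% to 20% of treated patients are non-responding toxicity cases who are all replaced. These are upper figures for each assumed share; they shrink if some excluded patients would have responded or if not all are replaced. The direction does not depend on the exact rate, as long as excluded patients respond less often than the rest, which the scan timing makes likely. Which patients the restart sentence covers is a secondary ambiguity.

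**What to change.** In section 7.2, delete the statements that these patients are not evaluable and may be replaced. State instead that a patient interrupted or stopped for drug-related toxicity stays in the primary ORR denominator, counts as a non-responder unless a response is confirmed, and is not replaced. In section 10.3.2, state that such interruption or stopping is not a reason for exclusion from the per-protocol set; otherwise the same patients could still be lost there. Also say which patients the restart sentence in 7.2 covers: those with hyperglycaemia, those delayed for other reasons, or those for whom Table 4 requires permanent discontinuation. That clinical choice is the sponsor's.

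The cost is amendment wording in two sections. It needs no added patients or procedures, and fewer replacements. The observed ORR may be slightly lower. The error for the all-treated ORR stays at 0.047, and power stays at 0.805 if 30% is the all-treated target. If 30% was meant for evaluable patients, the sponsor should acknowledge the lower power or revisit the sample size.

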### 7.3 Follow-up for toxicities

All patients must be followed up for safety (adverse events and serious adverse events) for 30 days following the last dose of bimiralisib. Patients whose treatment is interrupted or permanently discontinued due to a bimiralisib-related adverse event, including abnormal laboratory value, must be followed until resolution or stabilization of the event, whichever comes first which includes all study assessments appropriate to monitor the event.

### 8 Concomitant therapy

### 8.1 **Permitted concomitant therapy**

Medications required to treat adverse events, manage cancer symptoms, concurrent diseases and supportive care agents, such as pain medications, anti-emetics and anti-diarrheal are allowed, except if specifically prohibited (see section 8.3).

The patient must be instructed to notify the investigational site about any new medications she/he takes after signing of the informed consent. All medications (other than study drug) and significant non-drug therapies (including complementary and alternative treatments, vitamins, physical therapy and blood transfusions) administered within the screening period and up to 30 days after last study drug intake must be listed on the concomitant medications/significant non-drug therapies CRF.

Medications include not only physician prescribed medications, but also all over-the-counter medications, oral herbal medications (prohibited, see section 8.3) and food or vitamin supplements.

# 8.2 Concomitant (permitted) therapies that may require caution

# 8.2.1 Effect on other drugs metabolized by CYP enzymes

Bimiralisib has a low potential to cause clinically relevant drug-drug interactions by inhibiting cytochrome P450 isoenzymes. However, the induction potential could not be assessed yet and a potential enzyme induction for CYP2B6 and 3A4 could not be ruled out. It is therefore advised to monitor the efficacy of concomitant medications that are pre-dominantly metabolized by these enzymes to ensure that the patients are not underexposed during concomitant treatment with bimiralisib.

# 8.2.2 Effect of other drugs to affect the metabolism of bimiralisib

The major route of bimiralisib excretion is metabolism via CYP1A2/1 as identified *in vitro* and confirmed by clinical data in healthy volunteers and patients. Concomitant administration of the CYP1A2 inhibitor fluvoxamine causes a two-fold decrease in bimiralisib clearance and a respective prolongation of the elimination half-life. Consequently, caution should be exercised if strong or moderate inhibitors (e.g. ciprofloxacin, enoxacin, fluvoxamine zafirlukast, methoxsalen, mexiletine, oral contraceptives) or inducers (phenytoin, rifampin, ritonavi, teriflunomide) of CYP1A2/1 enzymes are concomitantly given with bimiralisib. For an updated list of compounds known to cause clinically relevant interactions refer to

http://www.fda.gov/drugs/developmentapprovalprocess/developmentresources/druginteractionslabeling/ucm080499.htm

# 8.2.3 Oral contraceptives and hormone replacement therapy

Several human studies have shown that gonadal steroids contained in oral contraceptive pills (OCPs) or hormone replacement therapy (HRT) agents have a significant effect on CYP enzymes, generally inhibiting enzymatic activity including CYP1A2 [36]. Therefore, patients receiving OCP or HRT should be monitored more closely for bimiralisib related adverse events and patients should be advised to inform their physician if their treatment with OCP or HRT is changing as cessation can lead to a drop in bimiralisib concentrations.

# 8.2.3.1 Drugs with a known risk to induce torsades de pointes (TdP)

Drugs with a known risk of TdP should be used with caution. Lists of drugs that can prolong QT and induce TdP can be accessed at https://www.crediblemeds.org/index.php/login/dlcheck

# 8.2.3.2 Systemic corticosteroid treatment

Corticosteroid treatment during the study is limited to the following:

- If receiving corticosteroids prior to enrollment, patients must have been on a stable or decreasing dose of corticosteroids and no more than 8 mg dexamethasone (or equivalent) for at least 5 days prior to date of enrollment.
- If treated with steroids at the time of first bimiralisib dose, the steroids should be tapered and then eventually discontinued as soon as possible. Maintenance steroids to prevent adrenal insufficiency and pituitary insufficiency due to hypophysitis are allowed. Permanent steroids use for the treatment of hypophysitis is allowed.
- Local applications for treatment of e.g. rash, inhaled sprays for treatment of e.g. obstructive airways diseases, eye drops or local injections (e.g. intra-articular)
- A short duration of systemic corticosteroids for symptomatic reasons (e.g. of chronic obstructive pulmonary disease, etc.) corresponding at maximum to the anti-inflammatory potency of 4 mg dexamethasone per day

# 8.2.3.3 Gastric protection agents

Bimiralisib is characterized by a pH-dependent solubility. Medicinal products that increase the pH of the upper gastrointestinal (GI) tract may alter the solubility of bimiralisib and consequently its absorption. These agents include, but are not limited to, proton-pump inhibitors (e.g. Omeprazole), H2-antagonists (e.g. Ranitidine) and antacids. These agents are restricted during the bimiralisib treatment.

# 8.2.3.3.1 Appropriate washout of gastric protection agents

Bimiralisib can only be administered after the interruption of these medicinal products sufficient to terminate their effect. The time i.e. washout period, after the last day of intake of acid-reducing agents (ARAs) before treatment with bimiralisib can start, depends on the class of the ARA. H2 receptor antagonists (e.g. ranitidine, famotidine, cimetidine, nizatidine, roxatidine, lafutidine) and direct acting antacids (e.g. maalox, tums, mylox, rolaids), are short acting and 3 days is recommended as the sufficient washout period prior to bimiralisib therapy. Proton-pump inhibitors e.g. omeprazole, esomeprazole, lansoprazole, pantoprazole and rabeprazole, are longer acting and the half-life for recovery of acid secretion is up to 46 hours after treatment discontinuation. It is advisable to wait at least 5 half-lives for the full recovery of gastric acid secretion and therefore the recommended washout period of at least 10 days is recommended for the proton-pump inhibitors before bimiralisib therapy can start. Due to their long term action, use of PPIs is prohibited until the end of bimiralisib treatment.

### 8.2.3.3.2 Ranitidine-based mitigation strategy

If patients who are receiving bimiralisib require treatment to increase the pH of the upper GI tract, they can be treated with 300mg ranitidine given once daily at bed-time. Importantly, in this case patients will take bimiralisib on an empty stomach approximately 4 hours after lunch and remain fasted for at least 1 hour prior to an evening meal. If ranitidine is not acceptable for the patient, other H2 antagonists may be proposed at the equivalent dose [37].

# 8.3 **Prohibited concomitant therapy**

# 8.3.1 Other anticancer therapies (exception: surgical treatment of skin cancer)

Anticancer therapy (chemotherapy, biologic or radiation therapy, and surgery) other than bimiralisib must not be given to patients while the patient is enrolled in the trial. If such treatments are required for a patient, then the patient must be permanently discontinued from the study.

Refer to section 9.7.1 for the exception of surgical treatment of skin cancer.

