# 9 Study assessments and procedures

Planned time points for all study assessments and procedures are provided in the table of assessments (ToA) Table 2.

Screening / Baseline evaluations must be performed within 28 days prior to first administration of bimiralisib.

During the course of the study, test procedures should occur on schedule whenever possible. Screening and baseline assessments should occur within the indicated windows. Assessments scheduled for Day -1, Day 1 and Day 8 should be performed on this day unless specified otherwise. At all subsequent visits, associated assessments that occur +/- 3 days from the scheduled visit date will not constitute protocol deviations. Tumor assessments (except at baseline) may occur within +/- 3 days from the scheduled date.

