# 9.5.1 Time period and frequency for collecting AE and SAE information

SAEs will be collected from the signing of the informed consent form (ICF) until 30 days after the last dose of study drug.

AEs will be collected from the first dose of bimiralisib until 30 days after the last dose of bimiralisib.

Medically relevant occurrences that begin after obtaining informed consent but before the first dose of bimiralisib will be recorded on the medical history section of the CRF, not the AE section.

All SAEs will be recorded and reported to the sponsor or designee immediately (within 24 hours of awareness), as indicated in Appendix 2. The investigator will submit any updated SAE data to the sponsor within 24 hours of awareness.

Investigators are not obligated to actively seek AE or SAE after conclusion of the study participation. However, if the investigator learns of any SAE, including a death, at any time after a participant has discontinued from the study, and he/she considers the event to be reasonably related to the study intervention or study participation, the investigator must promptly notify the sponsor.

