# 9.7.1 Dermatologic Evaluations

Several studies indicate that PI3K/mTOR signalling plays a critical role in non-melanoma skin cancer, including actinic keratosis (AK) [39]. Analysis of human epidermal tumors showed that mTOR itself, as well as its downstream effectors 4EBP1, S6K, and AKTSer473 are phosphorylated at much higher levels in AK and squamous cell carcinoma (SCC) compared to normal skin [40, 41]. Moreover, reverse phase protein microarray analysis of SCC and AK revealed aberrantly activated mTOR pathways in the pre-cancerous and transformed tissues compared to normal skin [42]. Significant up-regulation of the PI3K/AKT/mTOR pathway was not only found in SCC and SCC *in situ*, but also in AK when compared to normal, healthy skin. Increased PI3K/mTOR pathway activity is observed after a short term UV-R and persistently detected in sun-damaged skin lesions [40, 43, 44].

In the present study, patients will have the option to undergo a standard of care (SOC) skin cancer screening exam by a collaborating, board-certified dermatologist during screening. If actinic keratosis (AK) or keratoacanthomas (KA) are identified, structured skin photography will be performed to map AK or KA lesions. Structured skin photography will subsequently be repeated every 6 weeks to document changes in lesion numbers and size.

These assessments will not impact or interfere with SOC clinical management of the lesions. Resulting data will be reported separately.

Minor surgical procedures are permitted while on bimiralisib. Concomitant systemic anticancer therapy is not permitted while on bimiralisib.

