# 9.12 Follow up period

# 9.12.1 Safety follow-up

All patients will be followed up for safety up to 30 days after last dose of PQR309. The end of this period is defined as the "end of study" (EOS). At EOS, the investigator should contact the patient to inquire about any AE observed/concomitant medication taken during this period. This maybe done via a phone call. Patients whose treatment is interrupted or permanently discontinued due to an adverse event, including abnormal laboratory value, must be followed until resolution or stabilization of the event, whichever comes first. This will include all study assessments appropriate to monitor the event.

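### The End of Study safety contact may be made on day 27, before the 30-day adverse-event period is over, and section 8.3.1 is not reconciled with that period

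*Protocol*

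**What the plan says.** **Safety period.** Protocol 7.3: "All patients must be followed up for safety (adverse events and serious adverse events) for 30 days following the last dose of bimiralisib". Section 9.12.1 repeats it: "All patients will be followed up for safety up to 30 days after last dose of PQR309". It calls the end of that period the end of study (EOS), when the investigator is to ask about events during the period. Section 9.5.1 collects AEs from first dose, and SAEs from consent, until 30 days after the last dose. Section 10.4.2.1 runs the on-treatment analysis period to the same day and starts the post-treatment period on day 31.

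**Timing of the contact.** Table 2 sets EOS at 30 days after the last dose with a window of +/- 3 days, and footnote 6 allows a phone call. EOS is the last column of the table. Section 9 adds a general tolerance for visits after Day 8: "At all subsequent visits, associated assessments that occur +/- 3 days from the scheduled visit date will not constitute protocol deviations".

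**Other anticancer therapy.** Section 8.3.1 says that such therapy "must not be given to patients while the patient is enrolled in the trial", and continues: "If such treatments are required for a patient, then the patient must be permanently discontinued from the study". Section 9.7.1 describes the ban differently: "Concomitant systemic anticancer therapy is not permitted while on bimiralisib". Section 9.10 lists reasons for withdrawal from study treatment, and other anticancer therapy is not among them. Section 9.5.1 adds: "Investigators are not obligated to actively seek AE or SAE after conclusion of the study participation".

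The SAP sections available cover hypotheses and sample size only and do not address any of this.

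**The concern.** The safety endpoints (overall SAEs, SAEs resulting in death, frequency of AEs) are counted to a fixed day, 30 days after the last dose. The one routine contact that gathers events after the End of Treatment visit is allowed before that day. An event that begins after an early contact belongs in the tables, but no planned step finds it.

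Section 8.3.1 raises a related question. Patients who stop for progression may start another therapy within the 30 days. The protocol foresees this: 9.3 ends tumor assessments when another antineoplastic treatment starts, and the TTF definition in 10.4.1 counts new treatment without documented progression. Neither says what happens to safety follow-up. A site that applies 8.3.1 word for word could close the patient's participation at that point, while 7.3 still requires follow-up to day 30. Sites could then follow patients for different lengths of time.

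**Working it through.** **1. The contact window.** Inputs: nominal day 30 and tolerance 3 days (Table 2; section 9); end of collection and of the on-treatment period, day 30 (9.5.1; 10.4.2.1). Days are counted from the last dose.

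- Earliest permitted contact: 30 - 3 = day 27.
- Latest permitted contact: 30 + 3 = day 33.
- Days of the period still to come after the earliest contact: 30 - 27 = 3 (days 28, 29 and 30).
- Share of the post-dose period: 3/30 = 10%.

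This is a per-patient maximum. If a fraction *f* of patients is contacted on day 27 and the rest on or after day 30, the share of post-dose days without a later routine contact is *f* x 3/30. With 29 patients the ceiling (*f* = 1) is 29 x 3 = 87 of 29 x 30 = 870 patient-days, again 10%. The documents do not say how contacts will be spread over the window, so the realised share lies anywhere from 0 to 10%.

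**2. What still catches events on days 28-30.** SAEs and bimiralisib-related AEs that are already open are followed to resolution or stabilization (9.5.3; Table 2, footnote 6), so those patients are contacted again. Section 9.5.1 also requires prompt notification of any SAE, including a death, that the investigator learns of after discontinuation and considers related. What remains is a new event on days 28-30 in a patient contacted early who has no open event under follow-up, unless it reaches the site by another route.

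**3. Section 8.3.1 beside the follow-up sections.**

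| Question | 8.3.1 | Elsewhere |
|---|---|---|
| How long is other therapy barred? | While enrolled; the end of enrollment is not defined | 9.7.1: while on bimiralisib (systemic therapy) |
| What is stopped? | The study | 9.10: study treatment |
| Does 30-day follow-up continue? | Silent | 7.3, 9.12.1: yes, for all patients |

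The literal chain has three steps. EOS is the end of the 30 days (9.12.1), so a patient on day 14, say, may still count as enrolled. Starting another therapy then triggers discontinuation from the study (8.3.1). After discontinuation and the conclusion of participation, 9.5.1 requires only passive reporting. That result contradicts 7.3, 9.12.1 and the collection period in 9.5.1 itself.

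**4. Size of the 8.3.1 point.** If a share *s* of patients started other therapy on day *d* and follow-up did stop there, the lost share of post-dose days would be *s* x (30 - *d*)/30. The documents give neither *s* nor *d*, so no figure follows from them.

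**The case against.** The strongest reply is that the 30 days are protected. Sections 7.3, 9.5.1 and 9.12.1 tie the period to the last dose, not to enrollment status, and make no exception. The window moves the contact and leaves the collection period where it is; it is symmetric, so day 33 is as permissible as day 27. Section 9.12.1 places the contact at the end of the period.

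On 8.3.1, the protocol often uses leaving the study to mean stopping bimiralisib. Section 9.9 schedules the End of Treatment visit for patients who stop bimiralisib by reference to study discontinuation. Section 12.6.1.1 discontinues patients from the study, yet its footnote allows the drug to be restarted. Section 8.1 records medications and significant non-drug therapies up to 30 days after the last intake, which presupposes continued contact. The narrower ban in 9.7.1 can be read as showing the intended scope.

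Most of this stands. A reader might infer that 30-day follow-up is cut short, that 8.3.1 takes patients with progression out of safety follow-up, or that event counts are therefore biased low by some percentage. The documents do not support those readings: no section waives the 30 days, and the rates needed for a percentage are absent.

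Two things survive the reply. A contact on day 27 cannot ask about days that have not happened, and a symmetric window does not change that for the patient contacted early. Loose use of the term also does not settle 8.3.1, because 9.5.1 uses discontinuation from the study for the point after which only passive reporting applies.

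**Conclusion.** The point holds in a limited form. Table 2 and section 9 permit the last routine safety contact up to 3 days before the AE/SAE and on-treatment period ends. For a patient contacted on day 27, 3 of 30 days (10%) have no later scheduled ascertainment. Across the trial the share lies between 0 and 10%, depending on a spread of contact dates that the documents do not give. This is a gap in ascertainment, not a shorter period.

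Separately, 8.3.1 conflicts on a literal reading with 7.3, 9.5.1 and 9.12.1, and its ban period differs from that in 9.7.1. This is an ambiguity that permits loss of follow-up; loss is not shown, and its amount cannot be computed. Only secondary safety endpoints are touched. The primary endpoint, type I error, power and sample size are unaffected.

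**What to change.** 1. **EOS window.** In Table 2, set the EOS contact to 30 days + 3, not before day 30, and exempt EOS from the general +/- 3 day sentence in section 9.
2. **Scope of collection.** State once, for example in 9.12.1, that AE, SAE and death collection to 30 days after the last dose applies to every treated patient, whether or not another anticancer therapy has started.
3. **Flagging.** Flag AEs that begin after the new therapy, using the start date from the record already required by 8.1. Confirm that radiotherapy and surgery are captured there, since 8.1 does not name them among its examples.
4. **Reconciliation.** Reconcile 8.3.1 with 7.3, 9.5.1, 9.7.1, 9.10 and 9.12.1 on what is discontinued and over what period the ban runs. When other therapy is allowed is a clinical decision for the sponsor and is not proposed here.

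The cost is a few sentences. No visit is added, because EOS may be a phone call. The scheduling window narrows from 7 calendar days (27 to 33) to 4 (30 to 33), and some AEs of the next therapy will be recorded and need the flag.
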